9.3.3 Vital Signs

Descriptive statistics and mean change from baseline will be determined for vital signs (blood pressure, heart rate, respiratory rate and body temperature) at each assessment time. Vital sign results will be reviewed for clinically notable abnormalities and patients exhibiting clinically notable vital sign abnormalities that were not present at screening or baseline will be listed.

9.4 Study Definitions

Survival, time to progression, time to treatment failure, and duration of response will be presented using Kaplan-Meier curves for each patient group

9.4.1 Survival

"Survival" is defined as the period of time from date of first study drug administration to the date of death or date patient withdrawn from study.

9.4.2 Time to Progression

"Time to Progression" is defined as the period of time from the date of first study drug administration to the date that the patient is withdrawn because of clinical or radiographic progressive disease or death from any cause.

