4. TREATMENT PLAN

4.1 Dose of INCB018424 and Treatment Cycle

This is a phase II study of oral INCB018424 in patients with relapsed/refractory AML, ALL, and MDS (including CMML), and blast phase or tyrosine kinase refractory CML. The starting dose of INCB018424 will be 25 mg po twice daily, which has been determined to be the maximum tolerated dose in patients with myelofibrosis with myeloid metaplasia and a dose that is tolerated for ten days in normal human volunteers.

INCB018424 will be administered orally at a dose of 25 mg BID for 7 days each week for 4 weeks (cycle number 1). Patients will be evaluated after 1 full cycle of therapy (28 days) for response. Responding patients or patients with stable disease will be allowed to continue on study at a dose of 25 mg INCB018424 BID until progression. The response assessment for the purpose of study statistical evaluation will be after two cycles (8 weeks) of therapy. Patients with progressive disease, based on clinical and laboratory evaluation, will, at the discretion of the Investigator, either be removed from the study or, as long as the 25 mg BID dose has been well tolerated, dose escalated to 50 mg INCB018424 BID. In instances of dose escalation to 50mg BID, patients will be evaluated after

1 full cycle of therapy (28 days) for response and toxicity. At that point, patients with continued progressive disease, based on clinical and laboratory evaluation, will be removed from the study. In instances of dose escalation, the response assessment for the purpose of study statistical evaluation will be after two cycles (8 weeks) of therapy at the 50 mg BID dose.

Patients with chronic phase CML who have failed at least 2 prior tyrosine kinase inhibitors and do not have a standard transplant option will be assessed for response after 3 months of therapy in the absence of loss of disease control and they may continue therapy if they demonstrate any clinical benefit. Patients with chronic phase CML will not be allowed to have the dose escalation as this population has less of a life-threatening disease situation.

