4.4 Duration of Therapy

In the absence of treatment delays due to adverse event(s), treatment may continue until one of the following criteria applies:

- Lack of objective response after 2 cycles of therapy (3 cycles if there is dose escalation to 50 mg BID after cycle 1) unless INCB018424 is considered to be of clinical benefit to the patient
- Intercurrent illness that prevents further administration of treatment
- Unacceptable adverse event(s)
- Patient decides to withdraw from the study, or
- General or specific changes in the patient's condition render the patient unacceptable for further treatment in the judgment of the investigator.

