9.4.3 Time to Treatment Failure

"Time to Treatment Failure" is defined as the period of time from the date of first study drug administration to the date of withdrawal from the study for any reason other than study closure.

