9.4.4 Duration of Response

"Duration of Response" is defined as the period of time from the date of first objective response to the date of progression. "Duration of Response" is defined for patients with an objective response only.

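### Time to progression is dated to withdrawal, so a progression on 25 mg BID that leads to escalation is recorded late and may go uncounted

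*Combined protocol and SAP*

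**What the plan says.** Section 9.4.2 starts TTP at the first dose and ends it at "the date that the patient is withdrawn because of clinical or radiographic progressive disease or death from any cause". For a living patient the event is therefore the withdrawal, not the finding of progression.

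Section 4.1 separates the two. Patients are evaluated after the first 28-day cycle. One with progressive disease is, at the investigator's discretion, either removed or, "as long as the 25 mg BID dose has been well tolerated, dose escalated to 50 mg INCB018424 BID". After one more 28-day cycle, "At that point, patients with continued progressive disease, based on clinical and laboratory evaluation, will be removed from the study". One group is outside this path: "Patients with chronic phase CML will not be allowed to have the dose escalation". Section 4.4 includes among its reasons to stop "Lack of objective response after 2 cycles of therapy (3 cycles if there is dose escalation to 50 mg BID after cycle 1"), with an exception for patients judged to benefit. It has no separate item for progression.

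Section 9.4 promises Kaplan-Meier curves for survival, TTP, time to treatment failure and duration of response. Survival runs to death or withdrawal (9.4.1). Time to treatment failure runs to "the date of withdrawal from the study for any reason other than study closure" (9.4.3). Duration of response is "the period of time from the date of first objective response to the date of progression", for responders only (9.4.4). Section 9.2.1 calls the efficacy analyses exploratory.

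On response, section 4.1 states: "In instances of dose escalation, the response assessment for the purpose of study statistical evaluation will be after two cycles (8 weeks) of therapy", counted at 50 mg BID. Section 9.2.1 ties the efficacy estimates to the expanded cohort's dose. Section 9.1.1 names no dose for its rule of at least one response in 10, or for the 30-patient rate.

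**The concern.** A curve labelled time to progression should drop when patients progress. Here a patient whose disease has progressed, and who is escalated for that reason, remains progression-free on the curve until a later withdrawal or death. The patients affected are those in whom 25 mg BID has just failed, so the curve is too high early on, where much of the information in relapsed or refractory leukemia is likely to lie. A reader of the published curve could not tell how much of the early plateau is disease control and how much is the dating rule.

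**Working it through.** **Plan's own figures.** The documents give no design figure for TTP. The section 9.1.1 figures concern response and reproduce: 1 − 0.85^10 = 0.803 for the stated 80% power with 10 patients, and 1.96 × √(0.15 × 0.85 / 30) = 0.128 for the stated half-width of 0.13. Neither depends on the TTP definition.

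**Dates for one patient.** Inputs are the 28-day cycle and the one-cycle check after escalation (4.1), and the 3-cycle stop (4.4). Visit windows are ignored.

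- Progression found at the end of cycle 1: day 28.
- End of one cycle at 50 mg BID: 28 + 28 = day 56. Removal for continued progression is dated here, 28 days after the first progression.
- Three cycles: 3 × 28 = day 84. An escalated patient without continued progression or response may stop here for want of response. If that is not recorded as withdrawal because of progression, the day-28 progression is not an event. The same applies to an exit for toxicity. Death on study is an event on either path.

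**Other endpoints, same patient, no prior response.** Survival and time to treatment failure both run past day 28, because the patient is alive and not withdrawn. Duration of response does not apply. So no curve in 9.4 uses day 28.

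**Effect on an arm.** The documents do not give q (share progressing at day 28) or e (share of those escalated), so the values below are assumptions. Deaths and censoring up to day 28 are taken as nil, and progressing patients who are not escalated are taken as withdrawn at once.

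- Progression-free just after day 28, by first progression: 1 − q.
- As written: 1 − q(1 − e).
- Overstatement: q × e.

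| q | e | By first progression | As written | Overstatement |
|---|---|---|---|---|
| 20% | 25% | 80% | 85% | 5 points |
| 40% | 50% | 60% | 80% | 20 points |
| 60% | 75% | 40% | 85% | 45 points |

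The middle row in 30 patients: 12 progress and 6 of them are escalated. As written there are 6 events and 24/30 = 80% progression-free; by first progression there are 12 events and 18/30 = 60%.

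**After day 56.** If a share c of escalated patients is removed for continued progression at day 56, and the rest neither die nor are coded as progression, the remaining gap is q × e × (1 − c). In the middle row this is 20, 10 or 0 points for c = 0, 50% or 100%, with all other patients taken as progression-free. This is a snapshot at day 56 and not a lasting difference.

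**Effect on a median.** Assume 30 patients, of whom 18 first progress at day 28, 6 at day 56 and 6 at day 84, with each escalated patient withdrawn 28 days late. With 4, 9 or 18 of the 18 escalated, the progression-free share after day 28 is 16/30 = 53%, 21/30 = 70% or 30/30 = 100% as written, against 12/30 = 40%. The median is 56 days as written and 28 days by first progression in all three cases.

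**The case against.** The strongest case is that the point carries little weight. TTP appears neither in the section 1 objectives nor in the section 9.2 list of efficacy variables. Escalation is discretionary, requires good tolerance of 25 mg BID and is closed to chronic-phase CML. Every arm-level figure above rests on assumed rates. All of that stands. It limits the size and importance of the error, but the dating rule is still wrong for each escalated patient.

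A second objection concerns the remedy: a first progression date needs a definition of progression. Section 6 defines progression only after hematologic improvement (6.1.4.4), and no marrow is scheduled between screening and Cycle 4, so a day-28 progression may rest on judgement. This also stands, and the fix must supply the criterion. Section 4.1 already relies on such a judgement to remove or escalate a patient.

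A reader might infer that progressions in escalated patients who do not progress further are never counted. The documents do not establish that. Section 4.4 has no separate progression item, so its non-response stop could be coded as progression. Patients kept on for benefit may become late events, and on-study deaths count. Possibly uncounted is as far as the text goes.

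A reader might also infer that the response rate or the 1-in-10 rule is in error. That too goes beyond the text. Section 4.1 gives a rule for each patient, one category per patient (9.5.2) is compatible with it, and 9.1.1 is merely silent on dose. Only the dose wording in 9.2.1 is in tension, and that calls for clarification.

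**Conclusion.** The TTP definition is wrong as written for patients, other than those with chronic-phase CML, who progress on 25 mg BID and are escalated. For a progression at day 28 followed by removal for continued progression, the date is about 28 days late. If the exit is not recorded as progression and no on-study death occurs, the progression is not counted. Both statements follow from sections 4.1, 4.4 and 9.4.2 without any assumed rate.

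The direction is also clear: the curve is too high from the first progression until the later date, and beyond it for any progression left uncounted. The size is not known. The 5 to 45 points and the 56 against 28 day median are illustrations under assumed progression and escalation shares. The harm is a misleading descriptive curve; no hypothesis test, sample size or stage-one calculation is affected. The dose basis of the response rate is a minor separate clarification.

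**What to change.** 1. In 9.4.2, define the event as the first documented progression at any dose, including one that leads to escalation, or death from any cause, whether or not the patient is withdrawn.
2. State the progression criterion. The clinical and laboratory determination that section 4.1 already uses to trigger removal or escalation would serve.
3. Censor patients without an event at their last disease assessment, and record the date of first progression. The present measure may be kept as a supplementary curve under its own name, time to withdrawal for progression or death.
4. In 9.4.4, say that duration of response runs to the first progression after that response. Otherwise a patient who responds after escalation could be given a progression date earlier than the response.
5. As a clarification, reconcile 4.1 with 9.2.1 by stating whether responses after escalation count toward the 1-in-10 rule and the 30-patient rate in 9.1.1. Report responses by dose at response, keeping the two-cycle assessment time of 4.1.

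The cost is one extra recorded date, a written progression criterion and censoring rule, and a somewhat shorter reported TTP. No visit is added, because sections 4.1 and 6 already require assessment at the end of cycle 1. No dose or escalation rule is proposed.

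### Time to Progression is dated at withdrawal because of progression, so progression in patients who stay on study is counted late or missed, and patients stopped for lack of response without progression are selectively censored

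*Combined protocol and SAP*

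**What the plan says.** Section 9.4.2 runs TTP from first dose to "the date that the patient is withdrawn because of clinical or radiographic progressive disease or death from any cause". Section 9.4 gives the method: "Survival, time to progression, time to treatment failure, and duration of response will be presented using Kaplan-Meier curves for each patient group". No section states a censoring rule for TTP.

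Section 4.1 describes two kinds of patient who remain on study:
- With response or stable disease: "Responding patients or patients with stable disease will be allowed to continue on study at a dose of 25 mg INCB018424 BID until progression".
- With progressive disease, at the investigator's discretion, the patient is either removed or, "as long as the 25 mg BID dose has been well tolerated, dose escalated to 50 mg INCB018424 BID". Escalated patients are evaluated after a further 28-day cycle and removed if progression continues. Chronic-phase CML patients may not be escalated.

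Section 4.4 lists reasons to stop. The first is "Lack of objective response after 2 cycles of therapy", or after 3 cycles if escalated after cycle 1, and it is waived if the drug is thought to be of clinical benefit. The others are intercurrent illness, "Unacceptable adverse event(s)", the patient's decision, and "General or specific changes in the patient's condition render the patient unacceptable for further treatment in the judgment of the investigator". Progression is not an item in this list.

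The study calendar in section 5.2 ends with the End-of-Study visit, held when treatment stops; no response visit follows. Time to Treatment Failure (9.4.3) counts every withdrawal except study closure. Section 9.2.1 calls the efficacy analyses exploratory.

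**The concern.** Two things go wrong when the event is a withdrawal rather than a finding.

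First, progression and withdrawal are different dates for anyone escalated under 4.1. The definition uses the later one. If the escalated patient eventually leaves for another reason, such as an adverse event, the earlier progression never enters the curve unless the patient dies.

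Second, a patient who stops for lack of response without progression has no TTP event and no later assessment, so Kaplan-Meier can only censor that patient. Kaplan-Meier assumes that those censored have the same outlook as those who remain. Here they leave because they have not responded, while responders stay.

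Both effects make progression look later than it is. One TTP curve is to be shown per disease group, with at most 30 patients in each, so the part after week 8 could rest on a small, favourable subset.

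**Working it through.** The plan states no figure for TTP. The design figures in 9.1.1 reproduce: 1 − 0.85^10 = 0.803 (80% power with 10 patients), and 1.96·√(0.15·0.85/30) = 0.128 (half-width 0.13 with 30). Only the 15% response rate and n = 30 are used below.

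**Event date under escalation (4.1 against 9.4.2).** Take progression found at the day-28 evaluation, escalation, continued progression at the evaluation 28 days later, and removal. Progression is documented at day 28; the 9.4.2 date is day 56, a delay of 28 days. Against an assumed median of 2 months that is 28/60.9 = 46%; against 3 months, 28/91.3 = 31%. The documents do not say how many patients will be escalated, so no bias for the whole curve can be given.

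**Censoring for lack of response.**

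Inputs:
- Responders: 15% (9.1.1 target), with an assumed median TTP of 9 months.
- Non-responders: 85%, with an assumed median of 2 or 3 months.
- Exponential times.
- A fraction p of progression-free non-responders stopped at day 56, that is τ = 56/30.44 = 1.84 months. The values of p are assumed.
- Other withdrawal of 10% per 2 months (assumed), unrelated to prognosis. It cancels from the Kaplan-Meier limit.

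Let S_R and S_N be the progression-free probabilities of responders and non-responders, and S(t) = 0.15·S_R(t) + 0.85·S_N(t). The true 6-month progression is 1 − S(6). The Kaplan-Meier curve tends to

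KM(6) = S(τ) × [0.15·S_R(6) + 0.85(1−p)·S_N(6)] / [0.15·S_R(τ) + 0.85(1−p)·S_N(τ)].

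For a non-responder median of 2 months: S_R(τ) = 0.868, S_N(τ) = 0.529, S(τ) = 0.579, S_R(6) = 0.630, S_N(6) = 0.125. The truth is 1 − (0.0945 + 0.1063) = 0.799. With p = 0.5, KM(6) = 0.579 × 0.1476/0.3548 = 0.241, so 1 − KM = 0.759, which is 4.0 points too low.

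| Non-responder median | p | True | 1 − KM | Shortfall (points) | At risk after day 56, of 30 | Responders among them |
|---|---|---|---|---|---|---|
| 2 months | 0 | 0.799 | 0.799 | 0 | 15.8 | 22% |
| 2 months | 0.25 | 0.799 | 0.784 | 1.5 | 12.7 | 28% |
| 2 months | 0.50 | 0.799 | 0.759 | 4.0 | 9.7 | 37% |
| 2 months | 0.90 | 0.799 | 0.652 | 14.7 | 4.8 | 74% |
| 3 months | 0 | 0.693 | 0.693 | 0 | 18.7 | 19% |
| 3 months | 0.25 | 0.693 | 0.682 | 1.1 | 14.9 | 24% |
| 3 months | 0.50 | 0.693 | 0.663 | 3.0 | 11.1 | 32% |
| 3 months | 0.90 | 0.693 | 0.573 | 12.0 | 5.1 | 70% |

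Simulation of the same model agrees to within about 0.003. With a 2-month median, the shortfall is about 0.9 standard errors at n = 30 for p = 0.9, and 0.4 for p = 0.5.

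A second simulation used different assumptions: non-responder median 8 or 12 weeks, responder hazard 0.3 times that of non-responders, response rate 5% to 30%, with and without adverse-event withdrawal linked to prognosis. The week-24 progression-free probability was 13 to 22 points too high if all non-responders stop at week 8, 1 to 5 if half stop, and 0 to about 2 if none stop.

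**Would counting lack-of-response exits as progression repair it?** In the first model, 1 − KM at 6 months then becomes 0.83, 0.85 and 0.89 (p = 0.25, 0.5, 0.9) against a true 0.80, and 0.75, 0.80 and 0.88 against 0.69. That is further from the truth than the plan's curve in five of the six cases. At 2 months it is 11 to 48 points too high, because of an artificial step at day 56.

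**The case against.** The case against a serious finding is strong, and much of it stands.

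- A reader might infer that every non-responder leaves at day 56. The documents do not say so: 4.1 lets stable disease continue until progression, 4.4 waives the rule for clinical benefit and allows 3 cycles after escalation, and chronic-phase CML is assessed at 3 months. Only near-full removal gives a large bias.
- A reader might also infer that patients who deteriorate are lost as censored. That is not shown. The 4.4 reasons do not exclude progression, and 9.4.2 accepts clinical progression, so worsening from disease can already be an event. What is missing is a rule for which label applies.
- It is tempting to treat lack of response as progression. Section 9.5.2 keeps stable and progressive disease apart, the calculation shows a worse estimate in most cases, and TTP would drift towards Time to Treatment Failure.
- With a 2-month median, the cumulative incidence of the defined event at 6 months is 0.65, 0.58 and 0.46 for p = 0.25, 0.5 and 0.9, well below 1 − KM. That gap is not a bias: it measures progression observed on study, a different quantity. The plan never equates the two.
- TTP is exploratory, enters neither the sample size nor the expansion rule, and is shown beside Time to Treatment Failure.

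None of this answers the event-date defect, and Time to Treatment Failure does not correct the TTP curve.

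**Conclusion.** The concern holds in a limited form. As written, 9.4.2 gives a wrong event date for any patient with progressive disease who stays on study under 4.1: 28 days late in the simplest case, or no event at all. This follows from the text and needs no assumption about rates, although its effect on the whole curve cannot be sized.

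The selective censoring is real but conditional. At 6 months progression is understated by about 1 to 4 points if a quarter to a half of the progression-free non-responders stop at week 8, by about 12 to 15 points if 90% stop, and by close to nothing if stable disease continues until progression. Apart from the 15% response rate, every input to these figures is assumed. That censoring happens at all is inferred from the method and the absence of later visits, not from a stated rule.

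Because the endpoint is exploratory, this is a minor to moderate point.

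**What to change.** In 9.4.2:
1. Define the event as first documented progression (clinical, laboratory or radiographic) or death from any cause. Date it when documented, whether or not the patient is withdrawn then, and include progression or death known after withdrawal.
2. Do not count lack of objective response in a patient with stable disease as progression. Censor patients without an event at their last response assessment.

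In the reporting:
1. Tabulate withdrawals by 4.4 reason in each disease group.
2. Beside the Kaplan-Meier curve, show the cumulative incidence of progression or death with non-progression withdrawal as the competing event, labelled as a separate quantity.
3. Add a sensitivity analysis that treats lack-of-response withdrawals as events, described as an upper bound on progression.

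Separately, reconcile 4.1 with 4.4 on whether a patient with stable disease and no objective response continues; the size of the censoring problem turns on it.

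The cost is wording, one table and a little more analysis per group, using progression dates and withdrawal reasons from the study record. No visits are added, so information after withdrawal will be incomplete and the report should say how much was available. TTP may look slightly shorter.

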5. STUDY PROCEDURES

5.1 Screening

The following procedures are performed during screening, staging and workup (Table 5.1, below). These procedures are to be performed within 4 weeks prior to study drug administration, except where indicated.

Table 5.1: Procedures During Screening, Staging and Workup

Procedures	Specifics
Informed consent	
Full History and Physical Examination	History – present illness, all surgeries, all other medical illnesses, review of systems, allergies, all prior therapy for cancer and concurrent meds; F Physical exam – record weight, and note abnormalities in any major organ system (including but not limited to neurologic, head and neck, lymph nodes, cardiovascular, pulmonary, abdomen, extremities), note and
	measure sites of disease
Vital signs (including temperature, pulse, and blood pressure)	
ECOG performance status	
Pregnancy test (females of child-bearing potential only)	At screening, within 2 weeks prior to first dose
Disease status (note: measurement of lesions assessed only by physical exam should be performed within 1 week prior to first dose)	Staging with bone marrow biopsy or aspirates.
Note: Bone marrow biopsy or aspirate within 4 weeks prior to first dose of drug in all patients. Cytogenetics, immunohistochemistry, and histochemistries performed as indicated.	Lumbar punctures or radiographic investigations as appropriate to the disease.
Serum chemistries (repeat if screening chemistries completed greater than 72 hours prior to the first dose)	Sodium, potassium, chloride, CO ₂ , blood urea nitrogen, creatinine, glucose, calcium, phosphate, magnesium, AST and ALT, total bilirubin, alkaline phosphatase, total protein, albumin, uric acid, lactic dehydrogenase
Urinalysis (including microscopic)	
CBC with platelets (repeat if screening test completed greater than 24 hours prior to the first dose)	
PT/aPTT	
Chest X-ray PA-LAT	
HIV, Hepatitis B and C	Results of test performed within past 3 months acceptable

PA-LAT = Posterior anterior - lateral.

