6. RESPONSE DEFINITIONS

Patients will be assessed for efficacy at the end of each 28 day cycle of therapy, +/-4 days for the first 3 cycles, then 3 monthly thereafter.

6.1 Acute leukemias, MDS, CML-BP, CMML:

- 6.1.1 Complete remission: The patient must be free of all symptoms related to leukemia and have an absolute neutrophil count $\geq 1 \times 10^9 / L$ and platelet count $\geq 100 \times 10^9 / L$, and normal marrow differential ($\leq 5\%$ blasts) in a normo- or hypercellular marrow.
- 6.1.2 Partial remission: CR with 6-25% abnormal cells in the marrow or 50% decrease in bone marrow blasts.
- 6.1.3 CRp: As per CR but platelet count <100 x109/L.
- 6.1.4 Hematologic Improvement (HI)

Hematologic improvement should be described by the number of individual, positively affected cell lines (e.g. HI-E; HI-E + HI-N; HI-E+ HI-P + HI-N).

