6.1.4.4 Progression/relapse after HI

One or more of the following: a 50% or greater decrement from maximum response levels in granulocytes or platelets, a reduction in hemoglobin concentration by at least 2 g/dL, or transfusion

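### The Time to Progression event in 9.4.2 omits laboratory progression and is dated at withdrawal, so it does not match how section 4.1 identifies progression and the curves would run too long

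*Combined protocol and SAP*

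**What the plan says.** Section 9.4.2 starts the TTP clock at the first dose and stops it on the date the patient is "withdrawn because of clinical or radiographic progressive disease or death from any cause". Laboratory or marrow findings are not named. Progression without withdrawal is not an event.

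Section 4.1 uses a different basis. At the starting dose: "Patients with progressive disease, based on clinical and laboratory evaluation, will, at the discretion of the Investigator, either be removed from the study", or, if that dose has been well tolerated, escalated and kept on study. After escalation, "patients with continued progressive disease, based on clinical and laboratory evaluation, will be removed from the study".

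The only explicit progression criterion in section 6 is 6.1.4.4, progression or relapse after hematologic improvement. It includes "a 50% or greater decrement from maximum response levels in granulocytes or platelets", a hemoglobin fall, or transfusion.

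Imaging appears in the screening table of section 5.1, which lists "Lumbar punctures or radiographic investigations as appropriate to the disease" and a chest X-ray. The study calendar in 5.2 shows the chest X-ray at screening only and no other imaging.

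Section 9.4 states the use of the endpoint: "Survival, time to progression, time to treatment failure, and duration of response will be presented using Kaplan-Meier curves for each patient group". Section 9.4.4 ends Duration of Response at the date of progression, without defining it.

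**The concern.** The rule that identifies progression during the trial and the rule that counts it in the analysis are worded differently. Laboratory evaluation is in the first and missing from the second; radiographic progression is in the second and missing from the first. In these diseases progression is looked for mainly in blood and marrow, so the omitted route is the one with the most data.

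The event is also tied to withdrawal. Section 4.1 expressly lets a patient with progression remain on study at a higher dose. That first progression is not an event on its own date, whatever evidence established it.

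At stake are the per-group TTP curves and any medians read from them. In both situations the event is missing or late, so the error runs in one direction: TTP looks longer than it was. Two analysts could also assign different event status to the same patient.

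**Working it through.** The plan states no figure for TTP, so there is none to reproduce. The design figures in 9.1.1 do reproduce: 1 − 0.85^10 = 0.803 against 80% power, and 1.96 × √(0.15 × 0.85 / 30) = 0.128 against the stated half-width of 0.13. They concern response and do not involve TTP. The check is therefore mainly of the text.

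**1. The provisions side by side**

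| Place | Basis for progression | Dated at |
|---|---|---|
| 4.1, starting dose | clinical and laboratory | cycle evaluation; removal or escalation follows |
| 4.1, after escalation | clinical and laboratory | cycle evaluation; removal follows |
| 6.1.4.4 | granulocytes, platelets, hemoglobin, transfusion | not stated |
| 9.4.2 | clinical or radiographic, or death | withdrawal, or death |
| 9.4.4 | undefined | date of progression |

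**2. What data exist for each route.** Blood counts are weekly in Cycles 1 to 3 and every two weeks afterwards (5.2, footnote h). Marrow is taken at screening, Cycle 4, Cycle 7 and every sixth cycle after that (footnote i). No on-treatment imaging is scheduled. The route 9.4.2 names has no planned data; the route it leaves out has frequent data.

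**3. Patient withdrawn for progression seen only in blood or marrow.** Read literally, 9.4.2 gives no event at withdrawal. Death remains an event. If death is captured, the event comes later than the progression. If it is not, the patient must be censored at some point, and sections 9.4 to 9.4.4 give no censoring rule. The calendar ends at an end-of-study visit and shows no survival follow-up; section 8 collects serious adverse events to 30 days after the last dose. Either way TTP is lengthened.

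**4. Patient who progresses and is escalated.** Under 4.1 the first evaluation follows a full 28-day cycle, and the next follows a full 28-day cycle at the higher dose. If progression is found at the first and the patient is removed for continued progression at the second, then:
- first documented progression: about day 28;
- event under 9.4.2: about day 28 + 28 = 56.

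A patient who stays on longer has a still later event. Chronic phase CML is unaffected here, because 4.1 does not allow escalation in that group.

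**5. Size on the curve.** Let d be the share of true events that are deaths and g the share of progressions shown by laboratory findings alone. Assume constant hazards, withdrawal at each progression, and censoring at withdrawal for the g share. Then

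share of events counted = d + (1 − d)(1 − g), and the median is multiplied by 1 / share.

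- g = 0: share 1.00, factor 1.00
- d = 0.4, g = 0.3: 0.4 + 0.6 × 0.7 = 0.82, factor 1.22
- d = 0.2, g = 0.5: 0.2 + 0.8 × 0.5 = 0.60, factor 1.67
- d = 0.2, g = 0.7: 0.2 + 0.8 × 0.3 = 0.44, factor 2.27

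Neither d nor g is in the documents, and the censoring is assumed. These lines show how the result depends on g; they do not estimate the bias in this trial.

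**The case against.** The strongest reply is that *clinical* in 9.4.2 already covers laboratory findings. Section 9.2 lists clinical response and cytogenetic response as the efficacy variables, although leukemia response in section 6.1 rests on counts and marrow blasts. Section 9.3 counts routine laboratory tests among clinical safety data. On that reading g is zero. Conversely, 4.1 says clinical *and* laboratory, so every progression under 4.1 might have a clinical component. This stands in part. A reader might infer that 9.4.2 deliberately excludes laboratory progression; it contains no such exclusion. But 4.1 lists the two terms separately, 9.2.1 separates clinical from hematological response, and nothing in section 9 settles the usage. The broad reading also leaves the escalation gap untouched.

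A second reply is that counting to withdrawal may be intended, since 4.1 restarts the response assessment after escalation. That restart concerns response only. Section 9.4.2 keeps the first dose as its origin and does not mention escalation.

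Third, Time to Treatment Failure (9.4.3) counts withdrawal for any reason other than study closure, so these withdrawals do appear on one planned curve. True, but that curve mixes in toxicity and patient choice, and it too is dated at withdrawal.

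Fourth, the consequence is limited. TTP is not named in the objectives or in the efficacy variables of 9.2, efficacy is described as exploratory, and no sample size or decision rule uses TTP. This stands fully.

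**Conclusion.** The inconsistency is real and should be corrected. Section 9.4.2 does not match 4.1 or 6.1.4.4 on what counts as progression, and it does not match 4.1 on when progression occurs. The direction of bias is upward for the descriptive TTP curves. The laboratory gap rests on the literal reading of 9.4.2; the escalation gap does not.

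Three stronger conclusions are tempting and go beyond the documents:
- *Patients with laboratory progression will be censored at removal.* No censoring rule is given, and death still counts if it is captured.
- *Imaging is confined to staging.* The screening table lists screening procedures and does not forbid later imaging. What can be said is that none is scheduled.
- *Median TTP is inflated by a particular factor.* The factors above depend on shares the documents do not supply, and the range starts at no inflation from this source.

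The primary objective, the 10-then-30 design and its stated precision are unaffected.

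**What to change.** Redefine the 9.4.2 event as the earliest of: first documented progressive disease on clinical or laboratory (blood or marrow) evaluation, consistent with 4.1 and section 6; radiographic progression where imaging was done; or death from any cause. Date progression at first documentation, whether or not the patient is then withdrawn. Use the same progression date to end Duration of Response in 9.4.4.

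This changes only what the analysis counts and when. It does not alter who is escalated or removed under 4.1.

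The cost is a short change of wording in two sections. No new data are needed, since the counts, marrow results and cycle evaluations are already planned. Reported TTP will be shorter. One limit remains: section 6 gives an explicit criterion only for progression after hematologic improvement, so the new wording aligns the sections but does not itself supply thresholds for other patients.
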